5.2.1. Safety Population

Safety population – all subjects who take at least one dose of any IP. Subjects will be summarized under the treatment arm and starting dose of CC-122 they initially received.

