Up to approximately 20 subjects will be enrolled to Arm A to assess an intrasubject dose escalation schedule for CC-122.

If $> 20\%$ (eg, > 4 of 20) of subjects meet the criteria for DLT within 28 days of initial escalation to a dose level, no further intrasubject dose escalation to that dose level will be permitted.

Early DLT Evaluation for Fixed-Dose Cohorts in Arms B and C:

An initial 3 subjects will be enrolled to each of the fixed-dose escalation cohorts in Arms B and C. A dose level will be considered tolerable if 0 of 3 treated subjects experiences a DLT during the DLT evaluation period of each respective group. If 1 of 3 subjects experiences a DLT, 3 additional subjects will be enrolled to that dose level. A dose will be considered the NTD when ≥ 2 out of 6 evaluable subjects in a cohort experience a DLT. If DLTs are observed in ≥ 2 out of

6 evaluable subjects at the first dose level, a lower dose combination may be explored after review of safety data by the SRC (see Section 8.2.1).

After full enrollment and completion of the DLT evaluation period of each dose level, the number and type of DLTs and AEs occurring during the DLT evaluation period will be evaluated. A dose level will be considered tolerated after discussion of these data by the SRC. Subsequent dose cohorts will only be authorized to open for enrollment following a consensus by the SRC. Subjects enrolled in lower CC-122 fixed-dose cohorts will be allowed to escalate immediately to the next higher CC-122 dose level upon SRC approval of the subsequent CC-122 dose. For example, if the SRC has declared the 1.0 mg dose level tolerable and confirmed the opening of the 1.5 or 2.0 mg dose level, the subjects in the lower combination, ie, 0.5 mg CC-122 dose level may escalate to 1.0 mg. The MTD is defined as the highest dose level below the NTD with 0 or 1 of 6 DLT evaluable subjects experiencing a DLT during the specified DLT evaluation period. If only 3 subjects have been enrolled at the last dose level below the NTD, 3 additional subjects will be enrolled. A dose level will be declared the MTD when at least 6 subjects have been enrolled and < 2 subjects have experienced a DLT at that dose level.

An intermediate dose (ie, one between the NTD and the last dose level before the NTD) or additional subjects within any dose cohort may be added to determine the MTD and RP2D more precisely.

Monitoring for Late Toxicities During the Dose Escalation Phase:

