Up to approximately 20 subjects will be enrolled to Arm A to assess an intrasubject dose escalation schedule for CC-122.

If > 20% (e.g., >4 of 20) of subjects meet the criteria for DLT within 28 days of initial escalation to a dose level, no further intrasubject dose escalation to that dose level will be permitted.

Early DLT Evaluation for Fixed-Doses Cohorts in Arms B and C:

An initial 3 subjects will be enrolled to each of the fixed-doses escalation cohorts in Arms B and C. A dose level will be considered tolerable if 0 of 3 treated subjects experiences a DLT during the DLT evaluation period of each respective group. If 1 of 3 subjects experiences a DLT, 3 additional subjects will be enrolled to that dose level. A dose will be considered the NTD when ≥ 2 out of 6 evaluable subjects in a cohort experience a DLT. If DLTs are observed in ≥ 2 out of 6 evaluable subjects at the first dose level, a lower dose combination may be explored after review of safety data by the SRC (see Protocol Section 8.2.1).

After full enrolment and completion of the DLT evaluation period of each dose level, the number and type of DLTs and AEs occurring during the DLT evaluation period will be evaluated. A dose level will be considered tolerated after discussion of these data by the SRC. Subsequent dose cohorts will only be authorized to open for enrolment following a consensus by the SRC. Subjects enrolled in lower CC-122 fixed-dose cohorts will be allowed to escalate immediately to the next higher CC-122 dose level upon SRC approval of the subsequent CC-122 dose. For example, if the SRC has declared the 1.0 mg dose level tolerable and confirmed the opening of the 1.5 or 2.0 mg dose level, the subjects in the lower combination, ie, 0.5 mg CC-122 dose level may escalate to 1.0 mg.

The MTD is defined as the highest dose level below the NTD with 0 or 1 of 6 DLT evaluable subjects experiencing a DLT during the specified DLT evaluation period. If only 3 subjects have been enrolled at the last dose level below the NTD, 3 additional subjects will be enrolled. A dose level will be declared the MTD when at least 6 subjects have been enrolled and less than 2 subjects have experienced a DLT at that dose level.

An intermediate dose (i.e. one between the NTD and the last dose level before the NTD) or additional subjects within any dose cohort may be required to determine the MTD and RP2D more precisely.

Monitoring for Late Toxicities during the Dose Escalation Phase:

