5.2.2. Dose Limiting Toxicity (DLT) Evaluable Population

DLT Evaluable population –

- Arm A: is defined as all subjects who completed at least one cycle of treatment and did not miss more than 5 days of CC-122 dosing during the first cycle are to be considered evaluable for DLT, unless the missed doses were due to IP related AE(s) or the cycle was not completed due to a DLT, in which case they remain evaluable for DLT.
- Arm B: is defined as all subjects who completed at least one cycle of CC-122 (Cycle 2 Day 1 through Cycle 2 Day 28) and did not miss more than 5 days of CC-122 treatment are to be considered evaluable for DLT, unless the missed doses were due to IP related AE(s) or the cycle was not completed due to a DLT, in which case they remain evaluable for DLT.
- Arm C: is defined as all subjects who completed at least one cycle of CC-122 (Cycle 1 Day 9 through Cycle 2 Day 8) and did not miss more than 5 days of CC-122 treatment are to be considered evaluable for DLT, unless the missed doses were due to IP related AE(s) or the cycle was not completed due to a DLT, in which case they remain evaluable for DLT.

Subjects will be summarized under the starting treatment arm and starting dose of CC-122 they initially received.

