- TEAEs leading to dose reduction of CC-122, of other combination drug (ibrutinib), of CC-122 or other combination drug, of CC-122 and other combination drug;
- TEAEs leading to dose interruption of CC-122, of other combination drug (ibrutinib and obinutuzumab), of CC-122 or other combination drug, of CC-122 and other combination drug.

As well as

- TEAEs by cycle of onset;
- Febrile Neutropenia, TFR, TLS by cycle of onset and overall;
- TEAEs related to CC-122, other combination drug (ibrutinib or obinutuzumab) and CC-122 and/or other combination drug, by cycle of onset;
- TEAE with onset from second to sixth CC-122 cycle leading to dose reduction/discontinuation of CC-122, of other combination drug (ibrutinib and obinutuzumab), of CC-122 or other combination drug, of CC-122 and/or other combination drug;
- TEAE by CC-122 cycle of onset and leading to dose reduction/discontinuation of CC-122, of other combination drug (ibrutinib and obinutuzumab), of CC-122 and/or other combination drug, of CC-122;
- TEAEs by maximum NCI CTCAE grade;
- TEAEs related to CC-122, other combination drug (ibrutinib or obinutuzumab) and CC-122 and/or other combination drug, by maximum NCI CTCAE grade;
- Common ($\geq 10\%$) TEAEs;
- Common ($\geq 20\%$) TEAEs;
- Common ($\geq 10\%$) TEAEs related to CC-122, other combination drug (ibrutinib and obinutuzumab) and CC-122 and/or other combination drug;
- Common ($\geq 20\%$) TEAEs related to CC-122, other combination drug (ibrutinib and obinutuzumab) and CC-122 and/or other combination drug;
- Selected TEAE of interest by aggregated terms;
- TEAEs by PT.

Selected TEAEs/ serious AEs (SAEs) of interest as determined by the mechanism of action, known class effects, or TEAEs observed to date will be summarized by treatment arm and dose cohort, and then grade or cycle of onset. Standardized MedDRA queries (SMQs) will be used in the search strategy for some of the selected AEs of special interest, intending to aid in case identification. The groupings of selected AEs,

described by one phrase or topic term will be determined by clinicians based on SMQ or relevant search terms and provided to statistician, prior to database lock.

The selected TEAEs of interest include:

- Cardiac Failure (SMQ)
- Embolic or Thrombotic Events (SMQ) including ATE (Sub-SMQ), VTE (Sub-SMQ), and Mixed Embolic and Thrombotic Events (Sub-SMQ)
- Hemorrhage (SMQ)
- Interstitial Pneumonitis (SMQ)
- Peripheral Neuropathy (SMQ)
- Tumour lysis (SMQ)

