- Febrile Neutropenia (PT)
- Tumour Flare (PT)

To facilitate clinical study report writing, a summary table of TEAEs by PTs treatment arm will also be provided.

In addition, the following listings will be provided as well:

- Listing of subjects who had treatment-emergent SAE by treatment arm, dose cohort, subject number, SOC, and PT;
- Listing of subjects who had TEAEs leading to permanent withdrawal of any study drug by treatment arm, dose cohort, subject number, SOC, and PT;
- Listings of subjects who had adverse events leading to study drug reduction or interruption
- Listing of all subjects who died.

Individual subject listing of AEs will be presented as well. In addition, a listing of overdose will be provided.

A summary table for the summary of deaths information will be presented.

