11.1.2. Dose-limiting Toxicities (DLTs)

DLT is defined as a treatment-related AE(s) occurring in Cycle 1 (the first 28 days of treatment with CC-122 and combination therapy) that meets one of the criteria defined in the Protocol Section 8.2.7. Subjects will be observed for early DLTs for 28 days following the initiation of CC-122 (for Arm A, Cycle 1 day 1 through Cycle 1 Day 28; for Arm C, Cycle 1 day 9 through Cycle 2 day 8, and for Arm B, Cycle 2 Day 1 through Cycle 2 Day 28) (DLT evaluation period).

A summary table of DLTs during DLT evaluation period will be presented by dose cohort and treatment arm including number and percentage of subjects having a DLT. The percentage of subjects having a DLT is based on the number of subjects who are CC-122 evaluable for DLT Evaluable population. Listing of AEs which meet dose limiting toxicity will be provided.

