17. APPENDICES

17.1. Dose Escalation Rules

Table 8: Intrasubject Dose Escalation and Fixed-Doses Cohort Escalation Rules

Arm	No. of subjects recruited	Number of subjects that meet the criteria for DLT	NTD
Arm A ^[a]	20	> 20 %	
Arm B ^[b]	3+3	≥2	Yes
Arm C ^[b]	3+3	≥2	Yes

Notes:

^[a] Intrasubject escalation.

^[b] Fixed-doses cohort escalation.

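### Arm A: DLTs are tabulated for Cycle 1 only and safety data are grouped by starting dose, so no planned table shows the DLT rate at the level escalated to

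*SAP*

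**What the plan says.** **The rule is per dose level.** Protocol 4.1 and SAP 4.1.1 set the same early-DLT limit for Arm A. If more than 20% of subjects (the example is more than 4 of 20) "meet the criteria for DLT within 28 days of initial escalation to a dose level", then "no further intrasubject dose escalation to that dose level will be permitted". SAP Table 8, "Intrasubject Dose Escalation and Fixed-Doses Cohort Escalation Rules", repeats the 20% criterion.

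**The tables are by starting dose and Cycle 1.**
- SAP 5.2.1, Safety population: "Subjects will be summarized under the treatment arm and starting dose of CC-122 they initially received".
- SAP 5.2.2, DLT Evaluable population: "Subjects will be summarized under the starting treatment arm and starting dose of CC-122 they initially received". Arm A evaluability is judged on the first cycle.
- SAP 11.1.2 defines the DLT period as "for Arm A, Cycle 1 day 1 through Cycle 1 Day 28" and plans one DLT table for it, by dose cohort and arm, plus a listing.
- SAP 5.1 keeps all safety data of Arm A subjects who later add ibrutinib or obinutuzumab under Arm A and the starting dose.
- SAP 11.1.1 plans AE tables by dose cohort, grade or cycle of onset, including "TEAE with onset from second to sixth CC-122 cycle leading to dose reduction/discontinuation of CC-122". None is by dose at onset.

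Protocol 10.7 says DLTs will be summarized by arm and dose level where appropriate. SAP Section 15, which lists changes from the Protocol's statistical section, does not mention this point.

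**The concern.** Grouping by starting dose suits Arms B and C, where each DLT table describes a fixed-dose cohort over its own DLT period. In Arm A the dose is designed to change within the subject, as often as every two weeks, so the starting dose says little about the dose a subject was taking when an event occurred.

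Two things follow. Toxicity that arises at 3.0 or 4.0 mg is displayed in a 1.0 mg column. The plan's own per-level limit also has no matching output: no table gives the number of subjects who reached each level or how many of them had a DLT there. Safety of the single agent is the Arm A primary objective. The starting-dose tables describe the escalation schedule as a whole, but a reader of the final report could not see from them at which dose the toxicity appeared.

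**Working it through.** **The plan's own figure.** 4/20 = 20.0%, which is not above 20%; 5/20 = 25.0%. With 20 subjects the limit is passed at 5 DLTs, in line with the stated more than 4 of 20.

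**Inputs.** Start at 1.0 mg, maximum 4.0 mg, steps of 0.5 mg no more often than every 2 weeks (Protocol 4.1, SAP 4.1.1); a 28-day window from first reaching a level (same sections); DLT table for Days 1-28 (SAP 11.1.2); CC-122 cycles of 28 days (SAP 17.2.2). Actual escalation dates are not given, so the fastest schedule and a 28-day schedule are both shown.

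**Fastest schedule, 1.0 mg starter.** Level 1.0 + 0.5k mg is reached on Day 1 + 14k, and its window ends on Day 28 + 14k, for k = 1 to 6.

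| Level (mg) | Window (days) | Days within Days 1-28 |
|---|---|---|
| 1.5 | 15-42 | 14 |
| 2.0 | 29-56 | 0 |
| 2.5 | 43-70 | 0 |
| 3.0 | 57-84 | 0 |
| 3.5 | 71-98 | 0 |
| 4.0 | 85-112 | 0 |

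- Covered: 14 of 6 × 28 = 168 window-days, or 8.3%.
- The windows together span Days 15-112, which is 98 days; 84 of these (85.7%) fall after the DLT table ends.
- Days 29-98 (70 days) lie in two windows at once.

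**28-day steps, 1.0 mg starter.** The first escalation is on Day 29, so coverage is 0/168.

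**Starters under earlier amendments.**
- 0.5 mg: seven windows (1.0 to 4.0 mg). 1.0 mg is reached on Day 15 at the earliest, so coverage is at most 14/196 = 7.1%, and at least half of the 1.0 mg window is missed.
- 0.25 mg, assuming a first step to 0.5 mg: eight windows, at most 14/224 = 6.3%. 1.0 mg is reached on Day 29 at the earliest, so its window is missed entirely.
- For both, coverage is zero if the first step comes after Day 28.

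**Does the cycle 2-6 table fill the gap?** CC-122 cycles 2-6 are Days 29-168, or 140 days. On 14-day steps a 1.0 mg starter spends 14 days at each of 2.0, 2.5, 3.0 and 3.5 mg and 84 days at 4.0 mg (4 × 14 + 84 = 140). On 28-day steps it is 28 days at each of 1.5, 2.0, 2.5, 3.0 and 3.5 mg (5 × 28 = 140). Either way five dose levels share one 1.0 mg column.

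**Illustration (assumed numbers).** Suppose 20 subjects start at 1.0 mg, 8 reach 3.0 mg, and 3 of those have a DLT within 28 days. The rate is 3/8 = 37.5% among subjects who reached the level, above the limit, but 3/20 = 15% among all starters, below it. If there were no Cycle 1 DLTs, the planned table would show 0/20. The documents do not say which denominator the rule uses when fewer than 20 reach a level.

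**The case against.** The strongest reply is that the SAP follows the Protocol. Protocol 4.1 makes Cycle 1 the Arm A DLT period, Protocol 8.2.7 ties most DLT criteria to 28 days from the first CC-122 dose, and Protocol 10.2 judges evaluability on the first cycle. The DLT sentence in Protocol 10.7 is qualified and sits in a paragraph about the first 28 days. The inconsistency therefore begins inside the Protocol. That stands, and it is why the DLT definition should be left alone and any per-level count labelled supplementary. It does not remove the gap, because both documents already apply the DLT criteria per level.

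Second, the 20% limit governs conduct. Safety was reviewed on an ongoing basis, enrollment has stopped, and no Arm A endpoint is a per-level DLT rate. This also stands: nothing here shows that the rule went unapplied, and the point concerns final reporting only.

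Third, for about 20 subjects individual events can be traced through the AE and DLT listings and the "Listings of subjects who had adverse events leading to study drug reduction or interruption". That is true of single events, but no per-level denominator is specified. Since SAP 11.1.2 defines a DLT as a Cycle 1 event, later ones may also be missing from the DLT listing.

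Fourth, the percentages are shares of days, not of events, and leave out the starting level. Including it gives (28 + 14)/(7 × 28) = 42/196 = 21.4%. That is a fair alternative summary, but the limit is worded for levels escalated to, and 2.0 to 4.0 mg remain at zero coverage.

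Finally, the table shells are not available, and the SAP's abbreviation list includes an escalation-level term. Neither overrides the explicit starting-dose rule in 5.2.1 and 5.2.2.

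**Conclusion.** The point holds. Followed as written, the SAP gives no table from which an Arm A DLT rate can be read for any level escalated to, and its AE tables show higher-dose toxicity under the starting dose.

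The coverage figures are bounds. They assume regular steps up to 4.0 mg, whereas escalation is discretionary and not mandatory in subjects who are benefiting; a subject who never escalates is unaffected. The 0.25 mg figures also rest on the assumed first step.

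The consequence is limited to descriptive safety reporting: no endpoint estimate or dose selection changes. It is worth correcting because it bears on the Arm A primary objective and the remedy is cheap.

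**What to change.** Keep the starting-dose tables, the Protocol DLT definition, and the Arm B and C DLT tables. Add to the SAP, for Arm A only:

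1. **AEs by dose at onset (the more important addition).** Supplementary tables of treatment-emergent AEs, and of those leading to reduction or discontinuation, by actual CC-122 dose at onset (last dose taken if interrupted). Use the number of subjects who reached each level as denominator, and give exposure time at that level. Show events after ibrutinib or obinutuzumab was added separately, as the exposure summaries already do.
2. **Per-level count.** Events meeting the event and grade criteria of Protocol 8.2.7 within 28 days of first reaching each level, set against the 20% limit and labelled supplementary. Use recorded DLT flags or a medical review of candidate events, and state the denominator.
3. **Overlap rule.** Charge an event to the dose at onset in the main count and to every open window in a sensitivity count.

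The cost is a SAP paragraph and a few tables for about 20 subjects. Dose modifications are already recorded (Protocol 8.2.9.2), doses actually taken are already used for cumulative dose (SAP 8.2), and PK is already grouped by actual dose (SAP 5.2.4). Some medical review of events after Cycle 1 is needed, because no recording of DLT status beyond Cycle 1 is visible. No Protocol change is required.

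The new tables need a note on their limits: small denominators, subjects appearing in several columns, overlapping windows, delayed toxicity charged to the later dose, and selection, since only subjects who tolerate lower doses reach higher ones.

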5.2.2. Dose Limiting Toxicity (DLT) Evaluable Population

DLT Evaluable population –

- Arm A: is defined as all subjects who completed at least one cycle of treatment and did not miss more than 5 days of CC-122 dosing during the first cycle are to be considered evaluable for DLT, unless the missed doses were due to IP related AE(s) or the cycle was not completed due to a DLT, in which case they remain evaluable for DLT.
- Arm B: is defined as all subjects who completed at least one cycle of CC-122 (Cycle 2 Day 1 through Cycle 2 Day 28) and did not miss more than 5 days of CC-122 treatment are to be considered evaluable for DLT, unless the missed doses were due to IP related AE(s) or the cycle was not completed due to a DLT, in which case they remain evaluable for DLT.
- Arm C: is defined as all subjects who completed at least one cycle of CC-122 (Cycle 1 Day 9 through Cycle 2 Day 8) and did not miss more than 5 days of CC-122 treatment are to be considered evaluable for DLT, unless the missed doses were due to IP related AE(s) or the cycle was not completed due to a DLT, in which case they remain evaluable for DLT.

Subjects will be summarized under the starting treatment arm and starting dose of CC-122 they initially received.

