Each subject will be permitted to dose escalate by 0.5 mg increments every 2 weeks based on investigator assessment of the individual subject's tolerability (ie, escalation to the next dose level requires no DLT or dose reduction at the current dose level in addition to meeting the criteria outlined in Section 8.2.8).

However, dose escalation per cycle is not mandatory if the subject is benefiting (ie, objective evidence of disease response based on absolute lymphocyte count [ALC] reduction or shrinkage in measurable lesions required) from their current dose in the absence of significant toxicities. Subjects who are enrolled to fixed dose cohorts (0.25 mg or 0.5 mg) in Arm A under earlier protocol amendments (ie, protocol amendment 3 or 4) will be allowed to undertake intrasubject dose escalations as described above.

Subjects in Arm A will have the option to receive the addition of ibrutinib or obinutuzumab if there is evidence of PD while on CC-122 monotherapy after the completion of the DLT evaluation and CC-122 in combination with these standard agents has been demonstrated to be safe in the context of this trial. These subjects will receive a maximum of 24 cycles of CC-122 (including prior CC-122 monotherapy). The dose of CC-122 may need to be decreased to the level that has been shown to be safe in Arms B or C per the SRC (ie, < 2 DLTs/6 subjects). Subsequent intrasubject escalation is allowed if higher doses of CC-122 have been deemed tolerable in Arms B or C. This option will also apply to subjects that have enrolled in Arm A prior to IRB/EC approval of Amendment 5 after discussion with the Sponsor Medical Monitor.

CC-122 will be administered starting on Cycle 1 Day 1 on a 5/7-day schedule (5 continuous days out of 7 days per week) up to a maximum of 24 cycles, or until disease progression, unacceptable toxicity, or discontinuation for any other reason, whichever is earlier. Each cycle consists of 28 days.

Subjects will be observed for early DLTs in Cycle 1 (DLT evaluation period). Monitoring for late toxicities necessitating dose reductions or discontinuations will be conducted during Cycles 2 through 6.

Arm B (CC-122 + ibrutinib):

The following arm will be evaluated in parallel to Arm A:

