8.2.7. Definition of Dose Limiting Toxicity (DLT)

National Cancer Institute CTCAE Version 4.03 are used as a guide for the grading of severity of adverse events (except as otherwise specified). Dose-limiting toxicities are described below:

- A non-hematologic AE that is clearly not related to disease progression, medical procedure or intercurrent illness and that commences within 28 days of first CC-122 dose and is \geq Grade 3 EXCEPT for:
 - Alopecia
 - Grade 3 rash of the acneiform or maculopapular type of not more than 4 days durations (with optimal medical management)
 - Grade 3 diarrhea or vomiting lasting less than 72 hours (with optimal medical management)
 - Grade 3 diarrhea requiring hospitalization and Grade 3 nausea or vomiting that required tube feeding, total parenteral nutrition, or hospitalization will be considered DLTs
- Tumor lysis syndrome (TLS), unless TLS does not progress to Grade 2 and resolves in less than 7 days with medical management
- \geq Grade 3 tumor flare reaction (per NCI CTC AE Version 3.0)
- Laboratory abnormality that is clearly not related to disease progression, medical procedure or intercurrent illness and that commences within 28 days of first dose of CC-122 and is \geq Grade 3 (unless otherwise specified below)
- Hematological toxicities as follows (grading as per IWCLL criteria):
 - Any febrile neutropenia
 - Grade 4 neutropenia lasting > 7 days
 - Any Grade 3 or 4 thrombocytopenia with clinically significant bleeding
 - Any cytopenia that requires dose reduction during the DLT evaluation period
- Grade 4 liver function tests or Grade 3 ALT with Grade 2 or higher bilirubin will be considered a DLT irrespective of underlying attribution
- Any AE assessed as clearly not related to disease progression, medical procedure or intercurrent illness and necessitating dose-level reduction during the DLT evaluation period.

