8.6. Investigational Product Compliance

Subjects will return all IP at the Day 1 scheduled visit of each cycle to assess treatment compliance. Subjects must miss no more than 5 scheduled doses of IP during the DLT evaluation period (eg, forget to take or lose their IP; or if discontinued early due to progressive disease) to be considered evaluable for DLT, unless the missed doses were due to IP-related AE(s), in which case they remain evaluable for DLT. During subsequent cycles, a subject will be considered compliant with each IP and overall if the IPs taken are $\geq 80\%$ to $\leq 120\%$ of the assigned dosage. IP accountability will be evaluated on Day 1 of each cycle; full and/or partial bottles may be re-dispensed once IP accountability has been performed.

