10.2. Study Population Definitions

For the purpose of statistical analysis and data presentation, the study populations are defined as follows:

- Safety Population – all subjects who take at least one dose of IP.
- Dose-Limiting Toxicity Evaluable Population –
 - Arm A: all subjects who completed at least one cycle of treatment and did not miss more than 5 days of CC-122 dosing during the first cycle are to be considered evaluable for DLT, unless the missed doses were due to IP related AE(s) or the cycle was not completed due to a DLT, in which case they remain evaluable for DLT.
 - Arm B: all subjects who completed at least one cycle of CC-122 (Cycle 2 Day 1 through Cycle 2 Day 28) and did not miss more than 5 days of CC-122 treatment are to be considered evaluable for DLT, unless the missed doses were due to IP related AE(s) or the cycle was not completed due to a DLT, in which case they remain evaluable for DLT.
 - Arm C: all subjects who completed at least one cycle of CC-122 (Cycle 1 Day 9 through Cycle 2 Day 8) and did not miss more than 5 days of CC-122 treatment are to be considered evaluable for DLT, unless the missed doses were due to IP related AE(s) or the cycle was not completed due to a DLT, in which case they remain evaluable for DLT.
- Efficacy Evaluable (EE) Population – all subjects who complete at least one cycle of their assigned treatment regimen, and have a baseline and at least one post-baseline efficacy assessment.
- Pharmacokinetic Population – all subjects who have at least 1 measurable CC-122 and/or ibrutinib concentration datum.

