11.2.3. Causality

The investigator must determine the relationship between the administration of IP and the occurrence of an AE/SAE as Not Suspected or Suspected as defined below:

Not suspected: Means a causal relationship of the adverse event to IP administration is **unlikely or remote**, or other medications, therapeutic interventions, or underlying conditions provide a sufficient explanation for the observed event.

Suspected: Means there is a **reasonable possibility** that the administration of IP caused the adverse event. ‘Reasonable possibility’ means there is evidence to suggest a causal relationship between the IP and the adverse event.

Causality should be assessed and provided for every AE/SAE based on currently available information. Causality is to be reassessed and provided as additional information becomes available.

If an event is assessed as suspected of being related to a comparator, ancillary or additional IP that has not been manufactured or provided by Celgene, please provide the name of the manufacturer when reporting the event.

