5.2. Analysis Populations

All enrolled subjects will be used to assess subject disposition.

The demographic and baseline characteristics tables will use all populations defined in this section.

Drug exposure and all safety analyses (except for PK) will be based on the Safety population.

All DLTs will be based on the Dose Limiting Toxicity Evaluable population.

Efficacy analyses including Eastern Cooperative Oncology Group (ECOG) performance status (except for PK) will be based on the Safety population. Key Efficacy analyses [summary of ORR, DoR and PFS] will be based on both the Safety population and the Efficacy Evaluable (EE) population.

PK analyses will be based on the PK population.

All listings will use all enrolled subjects.

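### Having a DLT does not by itself make a subject DLT-evaluable, so the missed-dose and cycle-completion rules can remove an observed DLT from the DLT, NTD and MTD counts

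*SAP*

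**What the plan says.** For Arm A, SAP 5.2.2 asks for at least one completed cycle and that the subject "did not miss more than 5 days of CC-122 dosing during the first cycle". Arms B and C have the same rule, applied to their own 28-day CC-122 windows. A subject who fails the rule stays evaluable in two situations only: "unless the missed doses were due to IP related AE(s) or the cycle was not completed due to a DLT". Protocol 10.2 has the same pair of exemptions, the second being "or the cycle was not completed due to a DLT, in which case they remain evaluable for DLT".

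Protocol 8.6 states the missed-dose rule again with a single exemption: "unless the missed doses were due to IP-related AE(s), in which case they remain evaluable for DLT". It gives forgetting or losing the product, and early discontinuation for progression, as examples of disqualifying misses.

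SAP 5.2 then fixes the analysis set: "All DLTs will be based on the Dose Limiting Toxicity Evaluable population". Protocol 8.2.5 and 8.2.6 define the NTD and MTD on 6 DLT-evaluable subjects.

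The documents define a DLT in three ways. Protocol 8.2.7 excludes events clearly due to progression, a procedure or intercurrent illness, but adds: "Grade 4 liver function tests or Grade 3 ALT with Grade 2 or higher bilirubin will be considered a DLT irrespective of underlying attribution". SAP 11.1.2 requires a treatment-related event. Protocol 8.2.5 counts IP-related DLTs toward the NTD. Under protocol 11.2.3 an event may be rated as not suspected when "other medications, therapeutic interventions, or underlying conditions provide a sufficient explanation for the observed event".

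**The concern.** A missed-dose rule keeps under-exposed subjects from being counted as DLT-free. A subject who has already had a DLT has supplied the outcome, so low exposure afterwards is no reason to discard it. As written, the rule applies to that subject as to any other. If neither exemption fits, the event leaves both numerator and denominator of a primary endpoint. In cohorts of 3 to 6, a single event decides whether a dose is tolerated.

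**Working it through.** The plan gives no DLT rate or operating characteristic for dose escalation, so there is no stated figure to reproduce.

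**1. How easily the limit is passed.** CC-122 is given on "5 continuous days out of 7 days per week" (protocol 4.1). That is 4 × 5 = 20 scheduled doses in 28 days, and 5 missed doses is 5/20 = 25%, or one dosing week. Any gap longer than one dosing week exceeds the limit.

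**2. Which DLT subjects are lost under SAP 5.2.2 and protocol 10.2.**

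| Subject with a DLT in the window | Misses due to IP-related AE | Cycle cut short by the DLT | Status |
|---|---|---|---|
| Related DLT, long hold | yes | – | evaluable |
| DLT ends the cycle | – | yes | evaluable |
| DLT, then more than 5 days of forgotten or lost capsules | no | no | excluded |
| DLT, then early stop for progression or withdrawal | no | no | excluded |
| DLT under 8.2.7 rated not suspected, more than 5 days held, cycle completed | no | no | excluded |

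The last row matters only if protocol 8.2.7 governs. Under SAP 11.1.2 or protocol 8.2.5 that event is not a countable DLT in the first place. Under protocol 8.6 the exemption in the second row does not exist.

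**3. Effect of losing one DLT.**
- Arms B and C: 2/6 meets the NTD rule. Removing one DLT subject gives 1/5. Refilling the slot with a DLT-free subject gives 1/6, which is tolerated.
- Arm A: 5/20 = 25% is above the 20% limit. Removing one gives 4/19 = 21.1%, still above. Refilling with a DLT-free subject gives 4/20 = 20%, not above. The Arm A rule in protocol 4.1 speaks of subjects, not evaluable subjects, so it is affected only through the general statement in SAP 5.2.

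**4. Effect on the expected rate.** Let p be the true DLT rate. Let mD and mN be the probabilities of a non-exempt exclusion in subjects with and without a DLT. All three are assumptions. Excluded subjects are taken as replaced.

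- Rate among evaluable subjects: p′ = p(1−mD) / [p(1−mD) + (1−p)(1−mN)]
- Probability that the cohort is tolerated (0/3, or 1/3 followed by 0/3): P = (1−p′)³ + 3p′(1−p′)⁵

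With p = 0.33 and no loss: 0.67³ + 3 × 0.33 × 0.67⁵ = 0.301 + 0.134 = 0.434.

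With mD = 0.20 and mN = 0.05: p′ = 0.264 / (0.264 + 0.6365) = 0.293, and P = 0.508.

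The proposed rule sets mD = 0.

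| mD | mN | p′ as written | P as written | p′ with fix | P with fix |
|---|---|---|---|---|---|
| 0.05 | 0.05 | 0.330 | 0.434 | 0.341 | 0.413 |
| 0.10 | 0.10 | 0.330 | 0.434 | 0.354 | 0.390 |
| 0.10 | 0.05 | 0.318 | 0.458 | 0.341 | 0.413 |
| 0.20 | 0.05 | 0.293 | 0.508 | 0.341 | 0.413 |
| 0.30 | 0.05 | 0.266 | 0.565 | 0.341 | 0.413 |

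For mD = 0.20 and mN = 0.05 at other true rates, P moves from 0.709 to 0.764 at p = 0.20, and from 0.172 to 0.225 at p = 0.50.

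**The case against.** A reader might infer that a DLT subject is dropped for any missed doses not caused by an IP-related AE, and that the MTD is therefore biased upward. The documents do not support that, for these reasons:

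- **Most DLT subjects are protected.** The second exemption keeps those whose cycle was cut short by the DLT. Protocol 8.2.9.2 requires dose reduction or interruption for an IP-related toxicity that meets the DLT definition, so doses held for it fall under the first exemption.
- **The attribution route is narrow.** It needs protocol 8.2.7 to prevail over SAP 11.1.2 and protocol 8.2.5, and it needs a cycle with a long hold to count as completed, a term the documents do not define.
- **Direction is not fixed.** If non-exempt losses are equally likely with and without a DLT, p′ = p and P does not move. Forgotten or lost capsules have no stated link to toxicity, and the documents give no values for mD or mN.
- **Replacement is limited.** SAP 4.4 and protocol 10.3 provide for replacing non-evaluable subjects withdrawn before the window ends for reasons other than a DLT. A subject who completes the window with forgotten doses is not literally covered, so 1/6 is not automatic in that case.
- **The event stays visible.** AEs are tabulated in the Safety population. SAP 11.1.2 provides a listing of AEs meeting the DLT definition, and SAP 5.2 bases listings on all enrolled subjects. Under protocol 10.7 the Safety Review Committee has DLTs and all available safety information under review.
- **Enrollment closed on 05 Jul 2018.** No new cohort can be opened on this rule.

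These points stand, and they reduce the size of the problem. They do not remove it. Visibility in a listing is not inclusion in the count, and the exclusions after forgotten capsules, progression or withdrawal arise even under the SAP's narrower DLT definition.

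**Conclusion.** The gap is real and modest. No clause in SAP 5.2.2 or protocol 10.2 makes a subject evaluable because a DLT occurred, and protocol 8.6 contradicts 10.2 by omitting the DLT exemption. In a single cohort of six, one excluded DLT can change the NTD/MTD classification. On average the reported rate is shifted toward tolerated only if mD exceeds mN. The rise from 0.434 to 0.508 rests on an assumed true rate of 33%, assumed losses of 20% and 5%, and replacement of excluded subjects; it is not an estimate for this trial. With enrollment closed, the remaining effect is mainly on the reported DLT table and the NTD and MTD statements. It is worth correcting before database lock because the rule as written can delete an observed primary-endpoint event for no analytic gain.

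**What to change.** Add to SAP 5.2.2 and protocol 10.2, for all three arms: *Any subject who has a DLT during the DLT evaluation period is DLT-evaluable, whatever the number of or reason for missed doses and whether or not the cycle was completed. The missed-dose and cycle-completion exclusions apply only to subjects without a DLT.* Align protocol 8.6 with this wording. If no further protocol amendment is planned, record the change in SAP Section 15.

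Reconcile protocol 8.2.5, protocol 8.2.7 and SAP 11.1.2 so that one statement says whether a DLT needs IP attribution. Without that, the new sentence does not settle the not-suspected case.

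Cost: one sentence and one line of programming. The rule leans conservative, because DLT subjects are always kept while some DLT-free subjects are still excluded. With equal 10% loss at a true rate of 33%, the chance of declaring a dose tolerated goes from 0.434 to 0.390. The reported DLT rate may therefore look slightly less favourable.
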